1.1 Primary objectives

1.1.1 Perform a preliminary assessment of the efficacy of single-agent enzalutamide, based on overall response rate, in subjects with relapsed/refractory mantle cell lymphoma (MCL) or previously untreated MCL.

1.2 Secondary objectives

- 1.2.1 To evaluate the duration of disease control (progression free survival) in patients with MCL treated with enzalutamide.
- 1.2.2 To evaluate the safety profile of enzalutamide in MCL.
- 1.2.3 To gain preliminary data on clinical activity and toxicity of this regimen in male vs. female patients.

2.0 BACKGROUND

2.1 Mantle Cell Lymphoma (MCL)

MCL represents approximately 5-10% of non-Hodgkin lymphoma (NHL) diagnosed annually in the US and Europe, with an average incidence rate of approximately 0.5 cases per 100,000 person-years [1]. The average age at diagnosis is 70 and recent reports indicate, in contrast to other NHLs, the incidence of MCL is potentially on the rise [2]. Interestingly, and pertinent to this protocol, MCL demonstrates a clear male predominance with a male to female ratio ranging from 2-2.5:1 across multiple studies. Moreover, the aforementioned trend in increased incidence of MCL is largely accounted for by an annual percent increase in men (7.8%, vs 2.5% in women) [2]. The pathobiology underlying this gender-distribution imbalance is unknown, although anecdotal observations of decreased clinical aggressiveness of MCL in male patients who have been treated with androgen deprivation for prostate cancer (PCa) and in vitro evidence of relative androgen receptor (AR) overexpression in MCL cell lines implicate the AR signaling axis as a potential driver of leukemogenesis in MCL.

The clinicopathological features of MCL are intermediate between classically indolent and aggressive NHLs; demonstrating adverse features of aggressive lymphoma with frequent rapid disease progression, as well as adverse features of indolent lymphoma, being essentially incurable. As such, MCL presents uniquely challenging treatment paradigm which has garnered increased attention in basic and clinical research over the recent years. While these research efforts have led to approval of myriad new MCL-directed therapies (bortezomib, bendamustine, lenalidomide, ibrutinib) and improved clinical outcomes for patients afflicted with

this disease, MCL remains a largely incurable malignancy with a 3 year overall survival of 40-80% depending on age, gender and treatment regimen (i.e. chemoimunotherapy +/- ASCT) [3]. These data indicate that, despite improvements in therapeutic options for MCL, most patients will still relapse and eventually succumb to their malignancy. There exists, however, a subset of MCL patients that presents with an indolent form of the disease who are able to go months to years without MCL-directed therapy and whose long term prognosis is favorable. Defining patients with this indolent form of MCL at initial diagnosis is a clinical challenge and, thus far, there have been no clearly defined clinical or pathological features able to reproducible identify this subgroup; further prospective research is ongoing.

2.2 Enzalutamide and the AR axis in MCL

Sex steroid receptors are widely expressed in the hematopoietic system, and are characterized by sex-related differences, such as higher AR in leucocytes and macrophages from male donors [4, 5]. Steroid hormone signaling mediates pleomorphic effects, influencing dendritic cell, lymphocyte, NK cell, neutrophil, macrophage, platelet and red cell physiology [6-9], and resulting in gender-related differences in immune surveillance, cytokine production, and inflammatory responses [10]. Disease-specific differences in receptor expression have also been described, including aberrant methylation and expression of the AR in leukemia cells and non-Hodgkin's lymphomas (NHL) [11-13]. Of particular relevance to this protocol, the AR gene is preferentially hypermethylated (and therefore not expressed) in follicular and diffuse large B cell lymphomas, but remains unmethylated and open to transcription in MCL [14-15]. ER expression has also been demonstrated in human lymphomas, including Hodgkin's, Burkitt's and multiple myeloma cell lines[1] and ER signaling has been shown to modulate growth and proliferation in myeloma and Burkitt's cell lines[16, 17].

Preclinical studies at our institution have shown AR levels in MCL lines were $\sim 2^6$ fold higher than those in non-MCL cell lines or AR- PCa cell lines (Figure 1A). Additionally, expression of the AR target gene PSA in MCL cell lines was directly correlated with that of AR (Figure 1B) suggesting functional AR transactivation. Of note, lymphoma cell lines are known to express functional estrogen receptors, and although lower, AR transcript levels were within several fold of ER transcript levels in most MCL lines (Figure 1C).

[figure not shown]

Figure 1. (A) Expression of AR (white squares) and PSA (red triangles) by qRT-PCR in prostate cancer, mantle cell lymphoma (MCL) and non-MCL lymphoma cell lines (normalized to the house-keeping gene RPL13A). (B) Linear V regression of PSA and AR expression in the eight MCL lines and three non MLC lymphoma lines shown in A. (C) Concomitant expression levels of estrogen receptors alpha and beta in lymphoma lines.

Treatment of 4 different AR+ MCL lines with the AR agonist R1881, the potent AR antagonist enzalutamide (Section 3.1 below) or the combination demonstrated somewhat limited stimulation by agonist, but consistent suppression of proliferation by enzalutamide (Figure 2). Minimal change was observed in an AR negative MCL line (Ramos), and the magnitude of suppression in AR+ male and female MCL lines (Granta and Jeko, resp.) was comparable to that observed in the AR+ LNCaP PCa cell line. We detected AR, PSA and ER transcripts in human MCL tumors in the ranges observed in the panel of MCL cell lines (Figure 3, left), as well as variable but detectable levels of AR protein by IHC (Figure 3, right). In addition to this compelling preclinical data, in collaboration with our institution's GU oncology group and others, we have identified a very small subset of patient with both MCL and PCa on androgen-blocking therapies who have been observed anecdotally to have a more indolent course with regard to their MCL (personal communication); further informing the potential therapeutic role of AR axis blockade in patients with MCL.

[figure not shown]

Figure 2 Response of 4 AR+ MCL lines to treatment with control (hatched bars), the AR agonist R1881 (black bars), Enzalutamide (MDV3100, gray bars) or the combination (white bars), at 24, 48 or 72 hours, compared to the AR- non MCL lymphoma cell line, Ramos, and the AR+ prostate cancer cell line LnCaP. Gender of patients from which cell lines

[figure not shown]

Fig 3. Left – Expression of AR, PSA, ERa and ERb by qrt-pcr in replicate RNA isolates from tumor cells of 3 MCL patients. **Right** - Expression of AR by IHC in normal prostate, prostate cancer, negative isotype control, and 3 human MCL tumors (AR SC C-19) (different patients than those shown on left).

2.3 Summary

Despite recent advances in treatment strategies, MCL remains a largely incurable disease prone to short-interval relapses, ultimately resulting in a significant

foreshortening of quality adjusted life years for those afflicted with the disease. Based on the strong male predominance of MCL, the clinical observation of MCL tumor control following standard androgen deprivation therapy, and our preliminary data suggesting a role for AR-axis activity in MCL, we hypothesize that the potent AR antagonist enzalutamide will yield anti-tumor activity in MCL, induce downstream biological effects consistent with inhibition of steroid receptor signaling, and thus provide an additional effective therapeutic modality toward improving patient outcomes in this challenging disease process.

3.0 DRUG INFORMATION

3.1 General Information

Enzalutamide (MDV3100) is an androgen receptor signaling inhibitor that targets several steps in the AR signaling pathway. Enzalutamide competitively inhibits binding of androgens to ARs, inhibits nuclear translocation of receptors and inhibits the association of the AR with DNA. Enzalutamide is currently FDA approved for the treatment of metastatic, castration-resistant prostate cancer (CRPC). As this medication has not previously been studied in patients with MCL, we will extrapolate dosing and adverse effect monitoring from clinical experience with enzalutamide in the setting of CRPC. Enzalutamide is sold and distributed by Astellas/Medivation, Inc. under the brand name XtandiTM.

3.2 Administration

Enzalutamide is provided as liquid-filled soft gelatin capsule for oral administration. Each capsule contains 40 mg of the active pharmaceutical ingredient. The approved therapeutic dose (CRPC) is 160 mg once daily (4 capsules, each 40 mg).

3.3 Toxicity

3.3.1 Adverse events

The safety and tolerability of enzalutamide have been evaluated in a combined safety analysis including metastatic CRPC patients from 2 large randomized, placebo-controlled phase 3 studies (MDV3100-03) [NCT01212991] and CRPC2 [NCT00974311]). These data are summarized below. Please refer to the current FDA-approved package insert and/or the *Physician Desk Reference* for complete details.

The most common adverse reactions (\geq 10%) in patients with CRPC treated with enzalutamide are asthenia/fatigue, back pain, decreased appetite, constipation, arthralgia, diarrhea, hot flush, upper respiratory tract infection, peripheral edema, dyspnea, musculoskeletal pain, weight decreased, headache, hypertension, and dizziness/vertigo.

3 3 2 Seizure

Seizure occurred in 0.9% of patients receiving enzalutamide who previously received docetaxel and in 0.1% of patients who were chemotherapy-naive. Patients will be informed of the increased risk of

seizure and advised to inform their provider of any seizure or loss of consciousness. Patients who have a prior seizure history or chronic use of drugs that lower the seizure threshold will not be enrolled. Enzalutamide will be permanently discontinued for any subjects who develop a seizure during treatment.

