5.2 Exclusion Criteria

- 5.2.1 Uncontrolled illness including, but not limited to ongoing or active infection, symptomatic congestive heart failure, unstable angina pectoris, cardiac arrhythmia, or psychiatric illness/social situations that would limit compliance with study requirements within 6 months of enrollment.
- 5.2.2 Known active central nervous system lymphoma.
- 5.2.3 Known clinically significant heart disease as evidenced by:
 - Myocardial infarction within 6 months of enrollment.
 - Uncontrolled angina within 6 months of enrollment.
 - Congestive heart failure NYHA Class III or IV, or a history of congestive heart failure NYHA Class III or IV in the past, unless a screening ECHO or MUGA within 3 months results in a left ventricular ejection fraction ≥45%.
 - Clinically significant ventricular arrhythmias.
 - History of Mobitz II second degree or third degree heart block without a permanent pacemaker in place.
 - Bradycardia as indicated by a heart rate < 50 beats per minute at screening visit.
 - Hypotension as indicated by SBP \leq 85 on 2 consecutive measurements at screening visit.

- Uncontrolled hypertension as indicated by SBP > 170 mmHg or DBP
 > 105 mmHg on 2 consecutive measurements at screening visit.
- 5.2.3 Child Pugh class C hepatic dysfunction.
- 5.2.4 History of seizures.
- 5.2.5 Any life-threatening illness, medical condition, or organ system dysfunction which, in the investigator's opinion, could compromise the subject's safety, interfere with the absorption or metabolism of enzalutamide, or put the study outcomes at undue risk.
- 5.2.6 Patients with other prior malignancies except for adequately treated basal cell carcinoma, squamous cell carcinoma of the skin, breast or cervical cancer *in situ*, or other cancer from which the patient has been disease-free for 5 years or greater, unless approved by the protocol Investigator / Lead-Sub-Investigator.
- 5.2.7 Chemotherapy, immunotherapy, biologically targeted therapy, other investigational agent, or radiation therapy within 3 weeks of initiation of enzalutamide therapy. For patients with objectively progressive disease on a BTK-targeting agent whom in the opinion of the investigator would not tolerate a 21 day washout period, a >5 half-lives washout period will be allowed.
- 5.2.8 Prior allogeneic transplant with GVHD requiring ongoing immunosuppressive therapy.

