7.3 Prophylaxis

No prophylactic therapy is required for enzalutamide. Supportive care should be provided as clinically indicated.

7.4 Criteria for removal from protocol treatment:

- Documented progression of disease (see section 10.4).
- Development of seizures, or any therapy-related non-hematologic grade ≥ 4 toxicity or other serious adverse event as defined in section 12.0 will qualify for consideration of removal from protocol treatment.
- Development of any other unacceptable toxicity.
- Delay of treatment for more than 21 days due to toxicity.
- The patient may withdraw from the treatment at any time for any reason.
- Taking prohibited medications concurrent with enzalutamide therapy may result in removal from protocol treatment.

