8.0 DOSAGE MODIFICATIONS

8.1 Toxicity Management, Dose Modification and Dose Delay

If a patient experiences a \geq Grade 3 non-hematological toxicity related to the study drug or an intolerable side effect, treatment will be withheld for one week or until symptoms improve to \leq Grade 2 or baseline, at which point treatment will

be resumed at the same dose or at a reduced dose (120 mg or 80 mg), based on clinician judgment.

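### Section 3.3.2 requires permanent discontinuation after any seizure and bars users of seizure-threshold-lowering drugs, but 7.4 makes removal discretionary and 5.2 omits the drug exclusion

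*Combined protocol and SAP*

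**What the plan says.** Section 3.3.2 (Seizure) sets three rules on enrollment and discontinuation. Patients with a prior seizure history are not to be enrolled. Nor are patients on certain long-term medication: "chronic use of drugs that lower the seizure threshold will not be enrolled". For seizures on study the rule is unconditional: "Enzalutamide will be permanently discontinued for any subjects who develop a seizure during treatment".

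Three later sections deal with the same matters.

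- **5.2 (Exclusion Criteria)** lists "5.2.4 History of seizures" and nothing on drugs that lower the seizure threshold. Section 6.0 requires all Section 5 requirements to be met for registration.
- **7.4 (Criteria for removal from protocol treatment)** has a bullet that opens "Development of seizures, or any therapy-related non-hematologic grade", continues with grade 4 or higher toxicity and other serious adverse events, and ends by saying that these "will qualify for consideration of removal from protocol treatment". Another bullet in the same list reads simply "Delay of treatment for more than 21 days due to toxicity".
- **8.1 (Toxicity Management, Dose Modification and Dose Delay)** says that after a related non-hematologic toxicity of grade 3 or higher, or an intolerable side effect, treatment is withheld and will then "be resumed at the same dose or at a reduced dose (120 mg or 80 mg), based on clinician judgment". It makes no exception for seizure.

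**The concern.** Sections 3.3.2 and 7.4 give different instructions for the same event. The first requires a permanent stop. The second asks only that removal be considered, and its list is firmer on a 22-day toxicity delay than on a seizure. Section 8.1 widens the gap: a clinician who judged under 7.4 that removal was unnecessary would find in 8.1 a route back to treatment at the same or a lower dose.

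The drug exclusion is a different fault, an omission. A patient on long-term threshold-lowering medication can meet every criterion in Section 5 and still be someone whom 3.3.2 says must not be enrolled.

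What is at stake is patient safety: continuing or restarting enzalutamide after a seizure, or registering a patient at raised risk of one. Section 3.1 says that the drug has not been studied in mantle cell lymphoma before and that adverse-effect monitoring is extrapolated from prostate cancer, so these rules should read the same wherever they appear.

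**Working it through.** The plan states no figure on this point, so the main check is a comparison of texts.

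**Rule by rule**

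| Rule in 3.3.2 | Where it should reappear | What is found there |
|---|---|---|
| No enrollment with a seizure history | 5.2 | Carried over intact (5.2.4) |
| No enrollment with chronic use of threshold-lowering drugs | 5.2 | Absent |
| Permanent discontinuation after any on-treatment seizure | 7.4, 8.1 | Discretionary in 7.4; no exception in 8.1 |

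Intact: 1 of 3. Weakened: 1 of 3. Absent: 1 of 3.

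**Does the heading of 7.4 rescue the seizure bullet?** The heading alone would make any listed item a reason for removal, and that is how the progression and delay bullets work. The seizure bullet, however, has a predicate of its own, and seizures are its first subject. That predicate makes removal something to be considered.

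**How does the bullet compare with its neighbors?** Section 7.4 has six bullets: progression; seizure, grade 4 or higher toxicity or other serious adverse event; other unacceptable toxicity; delay beyond 21 days; patient withdrawal; prohibited medications. Only the seizure bullet speaks of consideration. The prohibited-medication bullet is also discretionary, but no other section makes removal mandatory in that case, so it creates no conflict.

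**Does another criterion in 5.2 cover the drug exclusion?** Criterion 5.2.5 begins "Any life-threatening illness, medical condition, or organ system dysfunction which" and then depends on the investigator's opinion. It concerns illness and organ function, not medication, so its cover is partial at best. Criterion 5.2.10 is confined to products with hormonal activity. Drug-based exclusions do belong in 5.2, since 5.2.7, 5.2.9 and 5.2.10 are all of that kind. Section 8.2.1 is not counted as a conflict: the drug sentence in 3.3.2 is an enrollment rule, and the table in 8.2.1 summarizes the metabolic interactions of 3.5.

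**How often might the 7.4 conflict arise?** Inputs: n = 20 (Section 11.0), and the seizure rates in 3.3.2 for prostate cancer patients, 0.1% without prior chemotherapy and 0.9% after docetaxel. Applying these rates to lymphoma patients is an assumption.

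- Expected seizures = n × p: 20 × 0.001 = 0.02; 20 × 0.009 = 0.18.
- Chance of at least one = 1 − (1 − p)^n: 1 − 0.999^20 = 0.020; 1 − 0.991^20 = 0.165.

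This is the chance that the conflict is put to the test, not the chance that a patient is wrongly continued. The documents give no rate of use of threshold-lowering drugs, so no figure can be given for the omission from 5.2.

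**The case against.** The strongest reply is that 3.3.2 is itself binding, specific and unconditional, and that nothing in 7.4 says a patient may continue after a seizure. An investigator can satisfy both sections by considering removal and then removing, so harm requires overlooking the protocol's own seizure section. That reading is available, and a careful reader of the whole protocol would act correctly. But 5.2, 7.4 and 8.1 are the sections written for registration, removal and dosing, and followed on their own they permit what 3.3.2 forbids. No rule of precedence is visible.

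It can also be said that 8.1 is a generic rule that carves out none of the removal criteria. That is correct, and it makes 8.1 a secondary gap, not a second conflict. Similarly, 6.0 makes the Section 5 criteria necessary for registration without calling them exhaustive, so the 5.2 point is a failure to carry a rule across and not a contradiction.

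Two further points stand. Section 3.3.2 neither defines chronic use nor names the drugs, so copying its phrase into 5.2 would carry that vagueness along. And the 16.5% figure applies the post-docetaxel rate to all 20 patients, although the trial also admits previously untreated patients; it is an upper end under an assumption, not a forecast.

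**Conclusion.** The concern holds. The conflict between 3.3.2 and 7.4 is enough to make the protocol wrong as written: the same event leads to mandatory permanent discontinuation in one place and to discretion in the other. The missing exclusion in 5.2 is a genuine omission, and the silence of 8.1 adds to the first problem.

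The point is worth correcting but limited in reach. It concerns safety wording and has no claimed effect on the response-rate benchmark or the futility rule. The triggering event is likely to be rare in a trial of this size, although the drug exclusion bears on every enrollment decision. The conclusion rests on the visible text only. The eligibility checklist named in 6.0 and the text just before 7.2 were not available, so nothing is asserted about the forms sites actually use; the visible wording of 3.3.2, 5.2 and 7.4 disagrees regardless.

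**What to change.** 1. In 7.4, take seizures out of the shared bullet and add a separate one: any seizure during treatment requires mandatory, permanent discontinuation of enzalutamide.
2. In 8.1, exempt seizure from the hold-and-resume rule, with a cross-reference to 3.3.2 and 7.4.
3. In 5.2, next to 5.2.4, exclude chronic use of drugs that lower the seizure threshold.

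Two additions are optional. A short definition of chronic use or a reference drug list would help sites apply the third change uniformly. Naming the drug class in 8.2.1 would cover drugs started on study; that would be a new safeguard, not the correction of a conflict.

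The cost of the three changes is a few words in each section. They exclude no one whom 3.3.2 does not already exclude and leave the sample size and analysis untouched. A drug list, if wanted, would take somewhat more work.

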3.3.3 Hypertension

Hypertension was reported in 10.6% of patients receiving enzalutamide and 4.3% of patients receiving placebo. No patients experienced hypertensive crisis. Patients will be informed of hypertension risk...

3.3.4 Falls and fall related injuries

Falls occurred in 9% of patients treated with enzalutamide compared to 4% of patients treated with placebo. Falls were not associated with loss of consciousness or seizure. Fall-related injuries were more severe in patients treated with enzalutamide and included non-pathologic fractures, joint injuries, and hematomas. Patients will be informed of fall risk.

3.3.5 Infection

1% of patients treated with enzalutamide compared to 0.3% of patients treated with placebo died from infections or sepsis. However, this increase in infection rate was not seen across all trials involving enzalutamide. Patients will be informed of potential increased infection risk.

3.3.6 Laboratory Abnormalities

Grade 1-4 neutropenia occurred in 15% of patients on enzalutamide (1% Grade 3-4) and in 6% of patients on placebo (no Grade 3-4). The incidence of Grade 1-4 thrombocytopenia was similar in both arms; 0.5% of patients on enzalutamide and 1% on placebo experienced Grade 3-4 thrombocytopenia. Grade 1-4 elevations in ALT occurred in 10% of patients on enzalutamide (0.3% Grade 3-4) and 18% of patients on placebo (0.5% Grade 3-4). Grade 1-4 elevations in bilirubin occurred in 3% of patients on enzalutamide and 2% of patients on placebo.

3.3.7 Hallucinations

1.6% of patients treated with enzalutamide were reported to have Grade 1 or 2 hallucinations compared to 0.3% of patients on placebo. Of the patients with hallucinations, the majority were on opioid containing medications at the time of the event. Hallucinations were visual, tactile, or undefined.

3.4 Pregnancy/Breast Feeding:

Enzalutamide is a pregnancy category X medication and is contraindicated in women who are pregnant or who are planning to become pregnant. A confirmed negative pregnancy test will be required for all female subjects prior to enrollment and both male and female subjects will be counseled on and required to employ effective use of barrier contraception from the start of therapy through a minimum

of 3 months after the last dose. Enzalutamide has not been studied in breast feeding mothers and its excretion characteristics in breast milk remain unknown. We will not enroll any patients who are actively breastfeeding.

